- To evaluate the safety of AMG 102 in combination with panitumumab
- Pharmacokinetics (PK) exposure of AMG 102 and panitumumab when given in combination

Part 2:

- To evaluate the safety and efficacy of AMG 102 (tolerable dose selected from part 1) in combination with panitumumab and AMG 479 in combination with panitumumab versus panitumumab alone
- PK exposure of AMG 102 and panitumumab when given in combination
- PK exposure of AMG 479 and panitumumab when given in combination
- PK exposure of panitumumab when given alone

Exploratory Objective(s):

The exploratory objectives will include, but will not be limited to the following:

Part 1:

- To evaluate the efficacy of AMG 102 in combination with panitumumab

Part 3:

- To evaluate the safety and efficacy of AMG 102 and AMG 479 monotherapy following treatment with panitumumab (cohort 3) in part 2
- Pharmacodynamic response of AMG 102 as assessed by hepatocyte growth factor/c-Met (HGF/c-Met), pathway markers, tumor apoptosis markers, angiogenic cytokines, and other biomarkers (Part 1, 2, and 3)

Approved

- Pharmacodynamic response of AMG 479 as assessed by insulin-like growth factor-1 (IGF-1), insulin-like growth factor binding protein-3 (IGFBP-3), and growth hormone (Part 2 and 3)
- Correlation between plasma HGF levels or tumor ribonucleic acid (RNA) expression, and tumor response (Parts 1, 2, and 3)
- Effects of tumor genetic variation in pathway genes, cancer genes, drug target genes, and other biomarker genes on subject response to investigational product (Parts 1, 2, and 3)
- Effect of genetic variation in cancer genes, drug target genes, drug metabolism genes, and other biomarker genes on subject response to investigational product on a subset of subjects. Separate pharmacogenetic informed consent required. (Parts 1, 2, and 3)

Hypotheses:

Part 1: Treatment with AMG 102 in combination with panitumumab will be safe and well tolerated.

Part 2: Treatment with AMG 102 or AMG 479 in combination with panitumumab will exhibit a greater ORR with acceptable safety than treatment with panitumumab alone.

Part 3: Hypothesis forming exploratory work will be undertaken to evaluate safety and efficacy among those subjects in part 2 that go on to receive AMG 102 or AMG 479 monotherapy in part 3.

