Study Design: This is a global, multicenter, open-label phase 1b and randomized, double-blinded 2-part phase 2 study designed to evaluate the safety and efficacy of AMG 102 or AMG 479 in combination with panitumumab versus panitumumab alone in mCRC subjects with wild-type KRAS tumor status.

Panitumumab will be open-label throughout the study (parts 1 and 2).

Investigational product will be administered every 2 weeks.

Part 1:

In part 1, approximately 6 to 18 subjects (6 to 9 subjects at each dose level of AMG 102 evaluated in combination with panitumumab) will be enrolled to receive open-label AMG 102 in combination with panitumumab with the purpose of identifying a tolerable dose of AMG 102 for the part 2 portion of the study.

AMG 102 10 mg/kg will be the starting dose evaluated in combination with panitumumab 6 mg/kg. Dose de-escalation of AMG 102 to 5 mg/kg will take place if determined necessary by the study team based on the interim safety analysis and incidence of DLTs. The dose of AMG 102 that is determined tolerable in combination with panitumumab in part 1 will be the selected dose used in part 2.

Subjects enrolled in part 1 will not be eligible for randomization in part 2.

Part 2:

Panitumumab will be open-label. AMG 102, AMG 479, and placebo will be blinded and will be referred to as blinded investigational product. In part 2, approximately 126 subjects will be randomized in a ratio of 1:1:1 to 1 of the following 3 double-blinded treatment groups. The randomization will be stratified for prior chemotherapy regimen received in the metastatic setting: irinotecan or oxaliplatin vs both.

Cohort 1: panitumumab 6 mg/kg and AMG 102 10 mg/kg (the tolerable dose selected from part 1 was 10 mg/kg)

Cohort 2: panitumumab 6 mg/kg and AMG 479 12 mg/kg

Cohort 3: panitumumab 6 mg/kg

Approved

Subjects randomized to cohort 3 of part 2 may be eligible to receive treatment with blinded investigational product in part 3 (see below).

Part 3:

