Upon radiographic disease progression per modified RECIST v1.0, clinical progression, or intolerance to all investigational products, subjects that meet the criteria outlined in protocol [Section 4.3](#) may be unblinded via the IVRS by the investigator or designated study staff to determine treatment assignment. Subjects randomized to cohort 3 (ie, panitumumab) of part 2 may be further randomized in part 3 in a ratio of 1:1 to 1 of the following 2 double-blinded treatment groups. The randomization will be stratified for reason for panitumumab discontinuation in part 2: disease progression (radiographic or clinical) versus intolerance.

Cohort 3a: AMG 102 10 mg/kg

Cohort 3b: AMG 479 12 mg/kg

The dose of AMG 102 (ie, 10 mg/kg) in part 3 will not be affected by the outcome of the interim safety analysis in part 1.

Investigational product will be administered every 2 weeks (Q2W) until disease progression, intolerance, withdrawal, death, or unless otherwise indicated by the study team (see investigational product administration details below).

All subjects that permanently discontinue all investigational products will complete a safety follow-up visit 30 days (+3 day window) and a follow-up visit 60 days (+14 day window) after the last dose of investigational product.

Subjects will be followed for radiographic disease progression (if not documented previously) and survival in the long-term follow-up portion of the study every 3 months (\pm 28 day window) after the 30 day safety follow up visit for up to 2 years after the last subject is enrolled in part 2.

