The subject treatment assignments in parts 2 and 3 will be unblinded after the planned data snapshot of the final analysis has been completed. Subjects receiving placebo will discontinue placebo administration and, in the absence of disease progression or unacceptable toxicities, may continue to receive investigational product (panitumumab AMG 102, or AMG 479, if applicable), Q2W at the investigator's discretion until disease progression, withdrawal of consent, death, or unless otherwise indicated by the study team. Data collection during this period will be limited to investigational product administration and serious adverse event reporting (see [Section 9.3](#)). Other protocol-specified procedures and observations outlined in the [Sections 7.1](#) through [7.6](#) and [Schedule of Assessments \(Appendices A and B\)](#), including blood samples and radiographic tumor imaging, will not be collected. However, the investigator, at his or her discretion, may continue to perform the procedures and observations outlined in the [Section 7](#) and [Schedule of Assessments](#) per local institution standard of care.

Primary and Secondary Endpoints:

Primary Endpoints:

Part 1: Subject incidence of DLTs

Part 2: Overall ORR

Secondary Endpoints:

Part 2:

- Duration of response
- Time to response
- Disease control

Approved

- Progression-free survival
- On-treatment progression-free-survival
- Overall survival
- Incidence of all AEs and clinical laboratory abnormalities
- Incidence of antibody formation to panitumumab, AMG 102, and AMG 479
- C_{\min} , C_{\max} , and AUC for panitumumab and AMG 102 (Part 1)
- C_{\min} and C_{\max} for panitumumab, AMG 102, and AMG 479 (Part 2)

Sample Size:

Part 1: Approximately 6 to 18 subjects (n = 6 to 9 per dose level of AMG 102 evaluated in combination with panitumumab).

Part 2: Approximately 126 subjects (n = 42 per cohort)

Part 3: Subjects from cohort 3 of part 2 will cross over to part 3 (n = 42)

Summary of Subject Eligibility Criteria:**Key Inclusion Criteria (Parts 1 and 2)**

- Man or woman \geq 18 years of age
- A life expectancy estimate of \geq 3 months
- ECOG 0 or 1
- Histologically or cytologically confirmed metastatic adenocarcinoma of the colon or rectum
- Wild-type KRAS tumor status of archival tumor tissue confirmed by an Amgen approved central laboratory or an experienced laboratory (local laboratory) per local regulatory guidelines using a validated test method

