Data collection for subjects who remain on study treatment after the planned data snapshot of the final analysis has been completed will be limited to investigational product administration and serious adverse event reporting (see [Section 7.7](#) and [Section 9.3](#)).

Statistical Considerations: Tolerability of AMG 102 in combination of panitumumab will be assessed in part 1 based on the subject incidence of DLTs. A subject will be considered DLT evaluable if the subject has received at least 2 doses of panitumumab and AMG 102 as scheduled (ie, Week 1 and 3) and has a minimum 4 week (28 days) follow-up for safety or has received at least 1 dose of panitumumab and AMG 102 and has a DLT within the first 4 weeks (28 days) on study. See [Section 2.5.3](#) for AMG 102 Dose Selected for Part 2.

Overall safety will be evaluated throughout the study including all enrolled subjects who receive at least 1 dose of investigational product (Safety Analysis Set). Efficacy will be evaluated on subjects in the Safety Analysis Set. The primary analysis for the ORR will include all enrolled subjects in part 2 in the Safety Analysis set with measurable disease at baseline.

The primary analysis for part 2 will occur after a minimum potential follow-up of 24 weeks after the last subject is randomized in part 2. All other available data will be summarized. ORR will be analyzed based on Bayesian methodology. Historical ORRs from 4 previous panitumumab trials combined with the response outcome from cohort 3 of the study will provide a posterior distribution for the overall panitumumab monotherapy ORR. A combination regimen may be considered promising and possibly warrant further evaluation in a larger subsequent study if the posterior probability that the odds ratio (ie, combination versus panitumumab alone) is greater than 1 is ≥ 0.90 . Likewise, a combination may not be considered promising if the posterior probability that the odds ratio is greater than 1 is ≤ 0.50 .

Approved

[figure not shown]
Final analyses will include data 2 years after the last subject is randomized in part 2.

Analyses will be separated by parts 1, 2 and 3.

Sponsor/Licensee: Amgen Inc.

Approved

Study Design and Treatment Schema

*In part 2, panitumumab will be open-label and AMG 102, AMG 479, and placebo will be double-blinded.

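### Part 2 adverse events: the supplied text names only incidence among dosed subjects, so differences in time on treatment can distort the comparison with panitumumab alone

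*Combined protocol and SAP*

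**What the plan says.** All references are to the most recent Protocol Synopsis in the file and its appendices.

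- **Endpoint.** Under Primary and Secondary Endpoints, the only part 2 entry for AEs is "Incidence of all AEs and clinical laboratory abnormalities". No unit of time at risk is attached.
- **Denominator.** Under Statistical Considerations, safety is evaluated in everyone who received at least one dose. The denominator is therefore subjects, not subject-time.
- **Comparison.** The part 2 secondary objective covers safety and efficacy of both combinations, "and AMG 479 in combination with panitumumab versus panitumumab alone". The part 2 hypothesis is that a combination "will exhibit a greater ORR with acceptable safety than treatment with panitumumab alone".
- **Duration.** "Investigational product will be administered every 2 weeks (Q2W) until disease progression, intolerance, withdrawal, death, or unless otherwise indicated by the study team". That sentence stands under the Part 3 heading of Study Design. Investigational Product Dosage and Administration states the same open-ended rule for the study generally.
- **After the last dose.** Every subject has a safety visit at 30 days (+3). Only cohort 3 may enter part 3, where the first dose may come as early as 2 weeks after the last part 2 dose (Appendix A & B, footnote o).
- **Size.** In part 2, "approximately 126 subjects will be randomized in a ratio of 1:1:1", giving 42 per cohort. Parts 1, 2 and 3 are analysed separately.

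No exposure-adjusted rate, time-to-first-AE analysis or common AE window appears in this text. The body of the protocol and the SAP are not in the file.

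**The concern.** Treatment ends at progression or intolerance, and both can be affected by the randomised drug. Time at risk for an AE is thus partly an outcome of treatment. A simple proportion of subjects with an event combines how fast events occur with how long subjects were exposed and observed.

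The distortion can run either way. A combination that delays progression looks more toxic than its event rate warrants. One that is stopped early for intolerance looks less toxic. Safety is part of the part 2 hypothesis, and part 2 is meant to inform whether a combination deserves a larger study, so an AE table that partly reflects duration could colour that judgement.

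**Working it through.** **Figures to reproduce.** The documents give no AE rate, treatment duration or safety threshold, so there is no safety figure to check. The sample size is consistent: 3 × 42 = 126.

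**Assumptions (none from the documents).** The AE hazard L is constant and identical in both cohorts. Time on treatment is exponential with median m months, so the stopping rate is mu = ln 2 / m. **From the documents:** AE observation continues for f = 30 days after the last dose, about 0.986 month, and n = 42.

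**Formula.** Expected incidence = 1 − exp(−L·f) × mu/(mu + L).

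**Main case: L = 0.10 per month, median 3 versus 5 months.**
- exp(−0.10 × 0.986) = 0.906.
- m = 3: mu = 0.231; 1 − 0.906 × 0.231/0.331 = 36.8%.
- m = 5: mu = 0.139; 1 − 0.906 × 0.139/0.239 = 47.4%.
- Gap 10.6 points, or 0.106 × 42 = about 4 subjects, with no difference in event rate.
- If observation stopped at the last dose (f = 0), the figures would be 30.2% and 41.9%, a gap of 11.7 points. The 30-day follow-up reduces the distortion only slightly.

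**Grid, follow-up included (gap in points).**

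| L per month | 3 v 4 | 3 v 5 | 4 v 6 | 3 v 6 |
|---|---|---|---|---|
| 0.05 | 4.4 | 8.3 | 7.4 | 11.8 |
| 0.10 | 5.8 | 10.6 | 8.9 | 14.7 |
| 0.20 | 5.9 | 10.4 | 8.1 | 14.0 |

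The range is 4.4 to 14.7 points; times 42, that is 1.8 to 6.2 subjects.

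**Opposite direction.** Suppose panitumumab alone has L = 0.10 and median 4 months (42.5%), and the combination has a hazard one third higher, L = 0.133. At the same 4-month median the combination would show 1 − 0.877 × 0.173/0.307 = 50.4%, about 8 points more. If it is stopped earlier, with median 3 months, it shows 1 − 0.877 × 0.231/0.364 = 44.4%, about 2 points more. Most of the real difference disappears.

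**Other inputs.** Setting the control cohort at 30% incidence with a 16-week median, 1.5 times the duration gives 37.9%, and 0.75 times gives 25.2%. Moving the control median between 8 and 24 weeks changes the 37.9% only to 37.0% or 38.3%. A near-universal AE at 90% moves only to 92.8% at 1.5 times the duration. An AE confined to the first weeks would hardly move.

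**Against sampling error.** In the main case the 95% CI half-width is 1.96 × √[(0.368 × 0.632 + 0.474 × 0.526)/42] = 21 points, wider than any gap in the grid.

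**Rate.** First events divided by time at risk estimates L, so the rate ratio is 1.0 at every duration ratio under this model.

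**A raw 12-week proportion does not suffice.** Twelve weeks is 2.76 months. Subjects still on treatment then are 0.5^(2.76/3) = 53% versus 0.5^(2.76/5) = 68%, so exposure already differs.

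**The case against.** The strongest objection is that this argues from silence. The evidence is one endpoint line in a synopsis, and exposure summaries or adjusted rates would normally be specified in the SAP body, which is not supplied. That stands. A reader might infer that the part 2 safety comparison rests solely on crude incidence. The documents do not support this: the endpoint says what is measured, without fixing the summary statistic or excluding others.

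A second tempting inference is that a go/no-go decision could flip. That is not supported either. The only decision rule in the text is on ORR (posterior probability that the odds ratio exceeds 1, at 0.90 and 0.50). Acceptable safety has no numerical trigger.

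It is also fair to say that incidence over treatment as actually given is a legitimate quantity, since subjects treated longer do experience more events. A rate answers a different question, which is why it belongs beside incidence and not in its place. The gaps are also smaller than the sampling error for any one AE, and all hazards and durations here are assumed.

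What remains is that the distortion is systematic. Unlike sampling noise, it pushes many time-accruing AE categories the same way at once, and a reader of incidence alone cannot separate it from toxicity. Separating the parts in analysis does not remove it. If AEs are assigned to part 3 from its first dose, which the text does not say, cohort 3 subjects who cross over could have only about 14 days of post-treatment observation against 30 in the other cohorts.

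**Conclusion.** The point holds as a limitation of the supplied text and a cheap improvement, not as a demonstrated error in the full plan. Incidence among dosed subjects is the only AE measure named, and with open-ended treatment it is not a comparison at equal exposure.

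Under a constant common hazard of 0.05 to 0.20 per month, exponential treatment times with medians of 3 to 4 versus 4 to 6 months, and 30 days of follow-up, equal event rates give incidence gaps of about 4 to 15 points (2 to 6 of 42 subjects). The effect reverses if a combination is stopped early, and is small for early or near-universal AEs. The consequence is confined to the descriptive reading of safety; no stated rule depends on it.

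**What to change.** Keep incidence as planned. Unless the full SAP already provides them, add for each part 2 cohort:

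1. Time on treatment.
2. First-event rates per subject-month at risk in part 2, with the difference from cohort 3 and its 95% CI. At-risk time should end at the first event or, without one, at the earlier of 30 days after the last part 2 dose and the first part 3 dose. This states explicitly how crossover subjects are counted.
3. For key AE categories and grade 3 or higher events, a time-to-first-event cumulative incidence estimate at one common early time point, for example 12 weeks. It should account for the end of at-risk time and for death, and should not be a raw 12-week proportion.

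The cost is two or three extra tables. AEs are reviewed at each visit and recorded on the eCRF (Appendix A & B, footnote d), and dosing is part of the schedule, so no new data or visits are needed. The downside is that the rate assumes a roughly constant hazard; item 3 is there for AEs where that is doubtful.

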
I agree to comply with the International Conference on Harmonisation Tripartite Guideline on Good Clinical Practice and applicable FDA regulations/guidelines set forth 21 CFR Parts 11, 50, 54, 56, and 312 and other applicable regulations/guidelines.

I agree to ensure that Financial Disclosure Statements will be completed by:

- me (including, if applicable, my spouse [or legal partner] and dependent children)
- my subinvestigators (including, if applicable, their spouses [or legal partners] and dependent children)

at the start of the study and for up to 1 year after the study is completed, if there are changes that affect my financial disclosure status.

I agree to ensure that the confidential information contained in this document will not be used for any purpose other than the evaluation or conduct of the clinical investigation without the prior written consent of Amgen Inc.

Signature

Name of Principal Investigator

Date (DD Month YYYY)

Approved

Protocol Synopsis

Title: A Randomized, Phase 1b/2 Trial of AMG 102 or AMG 479 in Combination with Panitumumab versus Panitumumab Alone in Subjects with Wild-Type KRAS Metastatic Colorectal Cancer

Study Phase: 1b/2

Indication: wild-type KRAS metastatic colorectal cancer

This protocol consists of 3 parts. Part 1 is the dose finding phase 1b portion of the study. Enrollment in part 1 was closed as of 04 May 2009. Part 2 is the phase 2, randomized, 3-cohort portion of the study. Enrollment in part 2 was closed as of 05 February 2010. Part 3 is an extension of the phase 2 (part 2) in which select subjects from part 2 may continue treatment in 1 of 2 cohorts. Throughout this protocol synopsis, the various portions of the study will be referred to as part 1, 2, or 3.

Primary Objective:

Part 1: To identify a tolerable dose of AMG 102 in combination with panitumumab based on the incidence of dose-limiting toxicities (DLTs). [Note: Enrollment in part 1 is now complete and a dose of AMG 102 (ie, 10 mg/kg) in combination with panitumumab has been identified for use in part 2. See [Section 2.5.3](#) for additional information on dose selected. The information for part 1 remains throughout this protocol for reference only].

Part 2: To evaluate the efficacy as assessed by the overall objective response rate (ORR) of AMG 102 (tolerable dose selected from part 1) in combination with panitumumab and AMG 479 in combination with panitumumab versus panitumumab alone

Secondary Objective(s):

Part 1:

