Appendix B. Schedule of Assessments (Part 3)

Study Procedures ^{a,r}	Qualification	Week	1	2	3	4	5	6	7	8	9	10	11	12	13	14	15	16	17	18	19	20
General Assessments																						
Review inclusion criteria for part 3 (see Section 4.3)	X ^o																					
Unblind in IVRS Note: only eligible subjects may be randomized in part 3 (see Section 7.2)	X ^o																					
Vital Signs ^b			X		X		X		X		X		X		X		X		X		X	
PE, weight & ECOG ^b	X	X			X			X							X			X				
Review of AEs, SAEs, & conmeds ^d	X		X	X		X		X				X		X		X		X		X		
Local Laboratory Tests^{f,r}																						
Hematology	X	X		X		X		X		X		X		X		X		X		X		
Chemistry ^g	X	X ^g		X	X ^g		X		X ^g		X		X ^g		X		X ^g		X ^g		X	
PT and INR		X			X								X								X	
HgbA1c	X	X			X				X						X				X		X	
TSH	X	X			X			X						X			X			X		
CEA	X							X ^t					X				X					
Central Laboratory Tests^{h,r}																						
Biomarker			X						X													
Antibodies ^{ip}		X					X															
Investigational Product Administration^r																						
Review dose adjustment criteria ^m				X		X		X		X		X		X		X		X		X		
Investigational product administration ^m		X		X		X		X		X		X		X		X		X		X		
Radiological Assessments^{n,r}																						
CT/MRI - Chest, Abdomen, & Pelvis									X				X			X		X				
Investigator Assessment of Tumor Response									X				X			X		X				

Approved

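### Does the part 3 sample size line, which has all 42 cohort 3 subjects crossing over, conflict with the conditional entry rule in a way that needs a change?

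*Combined protocol and SAP*

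**What the plan says.** The Sample Size section of the Protocol Synopsis (latest version) gives part 2 as "Part 2: Approximately 126 subjects (n = 42 per cohort" subjects, and the next line gives part 3 as "Part 3: Subjects from cohort 3 of part 2 will cross over to part 3 (n = 42". The part 3 line also appears in the earlier synopsis versions.

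The rest of the same version describes entry to part 3 as conditional:

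- The opening paragraph of the synopsis says that "select subjects from part 2 may continue treatment in 1 of 2 cohorts".
- Study Design, Part 2: "Subjects randomized to cohort 3 of part 2 may be eligible to receive treatment with blinded investigational product in part 3".
- Study Design, Part 3: after radiographic or clinical progression, or intolerance to all investigational products, subjects who meet Section 4.3 may be unblinded. Then, "Subjects randomized to cohort 3 (ie, panitumumab) of part 2 may be further randomized in part 3 in a ratio of 1:1". Allocation is stratified by the reason for stopping panitumumab.
- Appendix B, in the unblinding row: "only eligible subjects may be randomized in part 3".
- Footnote o to Appendices A and B repeats the permissive wording and sets a 2 to 6 week window for the first part 3 dose, with exceptions subject to sponsor approval.

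The part 3 hypothesis is exploratory and concerns safety and efficacy "among those subjects in part 2 that go on to receive AMG 102 or AMG 479 monotherapy in part 3". The Control Group entry says that part 3 has no control group.

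**The concern.** One line presents the full cohort as the number who will enter, while the surrounding text describes a gate that some subjects need not pass. A subject who dies or withdraws on panitumumab without qualifying, who does not meet Section 4.3, or who misses the dosing window does not reach part 3. The part 1 line gives a range and the part 2 line says approximately; the part 3 line has no such qualifier. A reader who stops at the Sample Size section would therefore take 42, or 21 per arm, as the planned size of part 3.

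If that number supported a comparison, a precision claim or a decision, the plan would rest on its best case. Anyone judging what cohorts 3a and 3b could show would overstate the information available.

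**Working it through.** **Inputs from the synopsis.** Part 2 total: approximately 126, randomized 1:1:1. Part 3 stated size: 42, allocated 1:1 to cohorts 3a and 3b. The available text gives no crossover fraction, power, precision target or decision rule for part 3.

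**Reproducing the figure.** Cohort 3 = 126 / 3 = 42. The stated part 3 size divided by the cohort size is 42 / 42 = 1.00. The arithmetic is right; the line gives the size of the source cohort as the number entering. With 42 entrants, 1:1 allocation gives about 42 / 2 = 21 per arm.

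**How unlikely is full crossover?** Assume that each cohort 3 subject enters independently with probability p. The expected number is 42p, and the chance that all enter is p^42.

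| p (assumed) | Expected to enter | Chance that all 42 enter |
|---|---|---|
| 0.90 | 37.8 | 0.012 |
| 0.95 | 39.9 | 0.116 |
| 0.99 | 41.6 | 0.656 |

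**What a smaller part 3 would do to precision.** For 0 events in n subjects, the exact two-sided 95% upper limit is 1 − 0.025^(1/n), taken here at the smaller arm under a near-equal split.

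| Crossover (assumed) | Part 3 total | Smaller arm | Upper limit for 0 events |
|---|---|---|---|
| 100% | 42 | 21 | 16.1% |
| 90% | about 38 | 19 | 17.6% |
| 80% | about 34 | 17 | 19.5% |
| 70% | about 29 | 14 | 23.2% |
| 50% | 21 | 10 | 30.8% |

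All rates in both tables are illustrative.

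**Does anything use the number?**

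1. *Entry to part 3.* Sites act on Section 4.3, Appendix B and footnote o, all of which are conditional. A sample size line does not randomize anyone.
2. *Recruitment.* Part 3 takes subjects only from cohort 3, and the current synopsis records part 2 enrollment as closed on 05 February 2010. There is no recruitment target for the figure to set.
3. *Part 3 analysis.* The hypothesis is already framed on the subjects who go on to receive monotherapy, so the analysis uses whoever entered.
4. *Part 2 primary analysis.* Objective response uses part 2 subjects in the Safety Analysis Set with measurable disease at baseline, and the Bayesian thresholds of 0.90 and 0.50 apply to the odds ratio against panitumumab. The size of part 3 does not enter.

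**The case for a change.** The strongest case for a change is that the synopsis disagrees with itself and that one line would put it right. The Sample Size section is where a reader looks for planned numbers, and the line survived several versions. Nothing in it tells the reader that 42 is a best case. That much stands: *will cross over* and *may be further randomized* do not say the same thing.

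Three supports for a stronger reading do not hold up.

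- Calling 42 a strict ceiling goes too far. Part 2 is approximately 126, so cohort 3, and with it part 3, could slightly exceed 42. Nor does the text guarantee an exact 21/21 split, so one arm could exceed 21.
- The rule for the period after the final data snapshot, under which subjects on placebo "in the absence of disease progression or unacceptable toxicities, may continue to receive investigational product", is weak evidence that cohort 3 subjects stay outside part 3. It covers parts 2 and 3 together, and the synopsis describes the part 3 product as active drug or placebo, so those on placebo may already be in part 3. It allows for a cohort 3 subject still on panitumumab but does not show that any was expected.
- The crossover rates are all assumed. They show how precision would vary, not that the plan counted on a particular value.

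Section 4.3 and the body statistical sections are not in the public text. They may give an expected crossover number, so the inconsistency can be established only for the synopsis.

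**Conclusion.** The wording slip is genuine and has no consequence. The figure of 42 is best read as the approximate number available to enter part 3 if every cohort 3 subject qualifies and goes on. An analyst or site reader will read it that way, because the conditional rule comes before the Sample Size line in the synopsis and is repeated after it.

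If 50% to 100% of cohort 3 entered, part 3 would have 21 to 42 subjects, and the upper limit for 0 events in the smaller arm would range from 30.8% down to 16.1%. That spread comes from an uncontrolled crossover extension and would be the same whatever the line said. Adding a qualifier such as *up to approximately* would keep the number and leave design, conduct, analysis and interpretation as they are.

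This conclusion rests on part 3 being exploratory and on the available text attaching no power, precision target or decision rule to its size. On that basis no change to the plan is called for.
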